#### 2. Trial registration

##### 2a Trial registration

The study will be registered at ClinicalTrials.gov: nr and date

##### 2b WHO Trial Registration Data Set

Data category	Information
Primary registry and trial identifying number	Clinical Trials
Date of registration in primary registry	23 January 2021
Secondary identifying numbers	Ethics Committee N-20200041
Source(s) of monetary or material support	Physiotherapy and Occupational therapy, Aalborg University Hospital
Primary sponsor	Physiotherapy and Occupational therapy, Aalborg University Hospital
Secondary sponsor(s)	Orthopaedic department, Aalborg University Hospital
Contact for public queries	[contact]
Contact for scientific queries	[contact]
Public title	The Achilles tendon Back-On-Track study. A randomised controlled trial on the effect of Early progressive strength exercise for treatment of acute Achilles tendon rupture.
Scientific title	A randomised controlled trial on the effect of Early progressive strength exercise for treatment of acute Achilles tendon rupture.
Countries of recruitment	Denmark
Health condition(s) or problem(s) studied	Achilles tendon rupture
Intervention(s)	Early progressive strength exercise programme
Key inclusion and exclusion criteria	Inclusion criteria: Patients with acute Achilles tendon rupture treated non-surgically. Diagnosed and treatment initiated within 3 days (of their injury). Age 18 – 65, able and willing to participate in the intervention. Able to speak and understand Danish

	Exclusion criteria: Achilles tendon rupture close to insertion on calcaneus or in the musculotendinous junction of the triceps surae. Previous Achilles tendon rupture or other conditions in either leg causing lower leg disability (pain, deficits in strength or range of movement). Treated with Fluoroquinolons or Corticosteroids within the last 6 months. Diabetes or rheumatic diseases. Severe medical illness: ASA score higher than or equal to 3 (ASA: American Society of Anesthesiologists physical status classification system)
Study type	Randomized controlled trial
Date of first enrollment	January 2021
Target sample size	82
Recruitment status	Not yet recruiting
Primary outcome(s)	Achilles Tendon total Rupture Score ATRS
Key secondary outcomes	ATRS, IPAQ short form, ATRA, Achilles tendon length, fear of re-rupture, adverse events, isometric strength and endurance, compliance, cost-effectiveness outcomes

### 3. Protocol version

Version 1.0 23Jan2021

### 4. Funding

The Physiotherapy and Occupational therapy department and Orthopaedic Surgery department at Aalborg University Hospital has guaranteed for the funding of the PhD study. This work was also supported by the Danish Physiotherapist Research Foundation, North Denmark Region Research foundation, AP Møller Lægefonden, Toyotafonden, Praksisfonden for fysioterapi, Danish Society of Sports Physical Therapy

## **5c Role of study sponsor and funders**

Sponsor is a part of the study, but is not involved in design, planning and analysis of the study. Sponsor will collaborate to ensure the right conditions for planning and conduct of the study and the publication of the results. Sponsor is non-commercial and declares no conflict of interest.

The funding sources will have no influence in the design of this study and will not have any role during the study execution, interpretation of the data or dissemination of results.

## **5d Composition, roles, and responsibilities of the coordinating centre, steering committee, endpoint adjudication committee, data management team, and other individuals or groups overseeing the trial, if applicable (see Item 21a for data monitoring committee)**

N/A

## **Introduction**

### **6. Background and rationale**

## **6a Description of research question**

Acute Achilles tendon rupture is a common injury and in Denmark the incidence has increased in recent years from 18.2/100.000 in 1984 and up to 31.17/100.000 in 2013.(1,2) Rupture usually occurs at age 30-50 with a male to female ratio 3-5:1.(1-3) The Achilles tendon is the largest and strongest tendon in the human body and is crucial for normal gait and running.(4) Historically surgical treatment has been favoured mainly because the re-rupture rates are lower compared to non-surgical treatment (3 vs 13%, respectively).(5,6) However, there is a risk of wound infection in surgical treatment compared to non-surgical and the results after a deep infection are often devastating.(7,8)

Regardless of choice of either surgical or non-surgical treatment, long-term muscular deficits and a decreased function after Achilles tendon rupture is found up to 7 and 10 years later.(9-11) The majority of the patients are of working age and a deficit in physical performance will have impact on returning to work and sports.(12-14) The risk of not being able to return to work or sport has potential influence on patients quality of life, risk of lifestyle diseases and healthcare economics.

There have been promising results in treatments using early functional rehabilitation (EFR) during the first eight weeks of treatment after both surgical and non-surgical treatment. The re-rupture rate with non-surgical treatment combined with EFR is reported similar to the rates with surgical treatment, which is an improvement compared to the former non-surgical treatment with immobilization.(7,15-18) The intention with early functional rehabilitation is to minimize the loss of muscle strength that is inevitable in the immobilizing period. Laboratory studies have also indicated that early loading of the ruptured tendon will improve the tendon healing in animals(19,20) and clinical studies have confirmed this.(21)

Several studies have reported use of controlled ankle/foot exercises, but few studies examined the effect of the exercises on its own and even fewer combined with non-surgical treatment.(22-25) We conducted a systematic review investigating the EFR used in the first 8 weeks of treatment and it showed very heterogeneous intervention protocols.(26) The components used in the EFR ranged from early weight-bearing and controlled range of motion ankle/foot exercises to strength exercises. The resistance exercises used in the early phase were most often isometrics, seated heel-rises or resistance exercises with an elastic band, but many studies did not describe the exercises and lacked information of exercise descriptors (eg. load, repetitions, sets) needed for a replication.(27)

Based on the results from this systematic review and our clinical expertise we designed a new, well-defined treatment protocol with exercises that were initiated earlier and with more progression than standard care today. We recently tested the feasibility of this new treatment protocol (N-20180072) which showed that the early initiation of exercises was highly feasible and patient acceptability was high. Based on our findings from 1) the systematic review and 2) our recently completed feasibility study, we now wish to test and compare this intervention to the current standard care that is delivered today. Such an intervention has the potential to negate the negative long-term functional consequences of Achilles tendon ruptures. By enhancing the physical function in the early stage, patients will have less sick leave and be able to return to work earlier. We expect that restoring early function could also positively benefit long-term outcome.

## **6b Explanation for choice of comparators**

The standard care exercise program is the standard treatment in the hospitals in the North Denmark Region. It is considered a safe treatment and well accepted in Denmark and in international literature. This program will be included in both study arms and the early progressive exercises will be an add-on to the standard treatment.

## **7. Objectives**

The purpose of this trial is to investigate the efficacy of standard care versus standard care combined with an early exercise program in improving the Achilles tendon Total Rupture Score ATRS(28) score 13 weeks after non-surgical treated Achilles tendon rupture.

We hypothesize that individuals with Achilles Tendon rupture randomized to standard care and early exercises will have a significantly higher ATRS score (primary outcome) after 13 weeks (primary endpoint) compared to individuals receiving standard care only.

## **8. Description of trial design including type of trial**

The trial is designed as a randomized, superiority trial with a 2-group parallel design with two centers. Reporting of the protocol follows the SPIRIT(29) statement and TIDieR(30) and CERT(31) for intervention description. The preparation of the trial, including publishing this trial protocol, was done in accordance with the PREPARE Trial guide. Before the inclusion of the first participant, the trial will be registered on clinicaltrials.gov.

Potential participants who are excluded during the physical examination and eligible participants who decide to withdraw before randomization will be asked to be part of a concurrent observational cohort.

## **Methods: Participants, Interventions, and Outcomes**

### **9. Study setting**

Participants will be recruited from the outpatient clinics at Orthopaedic department in Aalborg and Hjørring. Participants will attend baseline and complete the intervention at these two locations. The intervention will take place at the hospital and as home exercise. The physical follow-up will be done at Aalborg University Hospital after 9, 13 and 52 weeks. Links to the questionnaires used will be sent by REDCap (Vanderbilt University, Nashville, TN, USA)(32) to participants' e-mail address for 9, 13, 26 and 52 week follow-ups.

## 10. Eligibility criteria

Inclusion criteria:

- Patients with acute total Achilles tendon rupture treated non-surgically (Standard care of treatment in North Denmark Region)
- Diagnosed within 3 days (of their injury)
- Age 18 - 65, able and willing to participate in the intervention
- Able to speak and understand Danish

Exclusion criteria:

- Achilles tendon rupture close to insertion on calcaneus or in the musculo-tendinous junction of the triceps surae
- Previous Achilles tendon rupture or other conditions in either leg causing lower leg disability (pain, deficits in strength or range of movement)
- Treated with Fluorquinolons or Corticosteroids within the last 6 months
- Diabetes or rheumatic diseases
- Severe medical illness: ASA score higher than or equal to 3.(33)

Excluded patients and patients not willing to participate will follow the usual program of rehabilitation for non-surgical treatment at the hospitals.

## 11. Interventions

### 11a Interventions for each group with sufficient detail to allow replication

The exercise intervention take place while the participant is still in the immobilizing period with an orthosis. The exercises are designed as a daily home training program.

General information for both groups:

All participants receive general information about Achilles tendon rupture, tendon healing, choice of treatment and risks. The long-term prognosis of the Achilles tendon rupture is associated with lack of muscle strength and physical function and therefore forms the rationale for performing the exercise therapy. This information will be delivered both verbally and in a written leaflet.

A: Standard exercise program. Initiated at the 2-week (14 days) appointment in the outpatient clinic and a booster visit in the sixth week in the physiotherapy. The exercises are performed 5 times daily and with 25 repetitions:

- **Range of motion.** In the third week the participant is instructed to take the orthosis off and begin range of motion. The exercises are dorsal/plantar flexion and pronation/supination. For both exercises it is emphasized that dorsiflexion is restricted beyond neutral position of the foot. Position: seated with the foot hanging free from the chair and not resting on the floor. They carefully perform active dorsiflexion towards neutral and a passive plantarflexion. After one week gradually active plantarflexion is allowed.

- **Resistance strength exercise with elastic band.** In the sixth week the participant is instructed to do plantarflexion from neutral position with the resistance from an elastic band (low resistance). They are not allowed to pull the foot in dorsiflexion beyond neutral foot position. Position: seated with straight knee.

B: Standard exercise program plus add-on exercises. There will be an introduction to the exercises in week 2 (from day 7) and booster visits after 1 and 3 weeks. The sessions will be approx. 45 min.:

- **Range of motion (identical to standard care).** In the third week the participant is instructed to take the orthosis off and begin range of motion. The exercises are dorsal/plantar flexion and pronation/supination. For both exercises it is emphasized that dorsiflexion is restricted beyond neutral position of the foot. Position: seated with the foot hanging free from the chair and not resting on the floor. They carefully perform active dorsiflexion towards neutral and a passive plantarflexion. After one week gradually active plantarflexion is allowed.
- **Resistance strength exercise with elastic band (identical to standard care).** As in the standard treatment, **plus Add-on** that starts one week earlier and contains progression. In the fifth week the participant is instructed to do plantarflexion from neutral position with the resistance from an elastic band. They are not allowed to pull the foot in dorsiflexion beyond neutral foot position. They are instructed to progress by pulling the elastic band tighter or to change to a stronger elastic band. Position: seated with straight knee.
- **Isometric contraction.** In the second week while still immobilized in the orthosis the participant is instructed to do isometric contractions of the leg muscles/triceps surae. In the beginning it will be short time under tension (TUT) and low load and then progression as the participant feels comfortable. Progression of load will be a) allowing to push the forefoot against the bottom of the walker with more pressure, b) performing isometric contractions while standing. Position: can be seated, standing or lying down with bent or straight knee.
- **Seated heel-rise.** In the third week the participant is instructed to do a seated heel-rise while in the orthosis with the heel on the wedges and with open straps to allow movement. The wedges under the heel of the foot prevents excessive dorsiflexion of the foot. Progression is done with external weight on the knee. As the wedges are removed during the treatment the range of motion is increased. A book or a rolled towel is placed under the front of the orthosis to stabilize. Position: seated with bent knee in 90 degrees and possibly a cushion on the chair to compensate for the height of the orthosis with wedges. Alternative in the last three weeks is a supine pelvic lift combined with heelrise.
- **Progression:** The participant is instructed to progress the resistance exercises when they can. It is emphasised that the exercises must not cause sudden or severe pain in the tendon, but muscle soreness is to be expected. The exercise exertion should be within 2-5 on the Borg Scale.

Schedule of the exercise program and Exercise descriptors is presented in appendix.

Rehabilitation after the intervention period:

All participants are referred to rehabilitation in group sessions led by a physiotherapist from week 9 to 17. The program follows a standard protocol with exercises for strength and function progressing over time and there is advice for home exercise.

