### **11b Criteria for discontinuing or modifying allocated interventions**

Exercise sessions begin with assessing the progression of the tendon healing. In the first weeks with immobilization and physical examination is not possible, the participant is asked if there has been any constant or sudden pain or swelling and if there has been any excessive load to the tendon. At the 2-week appointment in the outpatient clinic the standard procedure is to examine any reported symptoms and perform a physical examination of the tendon and muscle structure.

In case of deviation from the protocol or adverse events, the Data and Safety Monitoring Board (see 21.a) will decide to either continue with modifications or to withdraw the participant from the study.

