The Tampa scale of Kinesiophobia (TSK) is used and validated for backpain, but has previously been used for Achilles tendon rupture evaluation as the questions about kinesiophobia could have associations to how patients with Achilles tendon rupture manage rehabilitation and return to sports.(40) The questionnaire consists of 17 items concerning pain and kinesiophobia and has 4 answers from “Strongly disagree” to “Strongly agree”. Measured at baseline, 9, 13 and 52 weeks.

Question: Were you afraid to do the prescribed load when performing the exercises? If yes why?  
Measured at 9 weeks

**Compliance with the intervention:** The participants will register the number of exercise sessions they perform each day in a training journal. The timeframe will be from the day they start the exercises to the end of week 9.

**Safety and Adverse events.** The number of serious and minor adverse events is registered in a pre-defined list based on Common Terminology Criteria for Adverse Events(43) and the participants will be asked open questions at each session. Serious adverse events are re-rupture, non-union of the tendon or symptomatic deep vein thrombosis (DVT). Muscle soreness or mild pain is considered inevitable and normal when initiating exercises after a period of immobilization.

**Cost-effectiveness outcomes.** To evaluate the cost-effectiveness of the intervention, we will use self-reported health state as measured by the EQ-5D-5L.(44) Work productivity outcomes are measured using the Work Productivity and Activity Impairment Questionnaire WPAI:GH and condition-related expenses as measured by a self-developed questionnaire. The EQ-5D provides a simple descriptive profile and a single index value for health status and has been used extensively in research to measure QALYs gained and thereby perform health economic evaluations. The questionnaires will be filled out during all follow-ups.

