### 22. Harms

All participants receive information about possible adverse events relative to the Achilles tendon rupture in general and to the specific intervention. In case of serious adverse events they are encouraged to seek immediate medical attention and for minor adverse events to contact the project physiotherapist by phone. At each session the participants will answer questions of possible adverse events during and between the sessions. During and after completion of the study the included participants will also be followed in the outpatient clinic and in The Danish Achilles tendon Database (DADB).

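### Adverse events are asked about at sessions, but arm B has 1–3 more dated contacts than arm A before week 7 and neither arm has a dated session in weeks 7–8, so minor events are collected unevenly

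*Protocol*

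**What the plan says.** **Sessions.** Protocol section 11a dates arm B's contacts as follows: "There will be an introduction to the exercises in week 2 (from day 7) and booster visits after 1 and 3 weeks". For arm A, the standard programme, it says: "Initiated at the 2-week (14 days) appointment in the outpatient clinic and a booster visit in the sixth week in the physiotherapy". Section 6b says of the standard programme: "This program will be included in both study arms". Arm B may therefore also attend the week-6 booster, though no section says so outright. Group rehabilitation starts in week 9 (section 11a), and the first physical follow-up is after 9 weeks (section 9).

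**Questions about harm.** Section 11b: "Exercise sessions begin with assessing the progression of the tendon healing". While the leg is immobilised and cannot be examined, the participant is asked about "any constant or sudden pain or swelling and if there has been any excessive load to the tendon". On safety outcomes, section 12 says "The number of serious and minor adverse events is registered in a pre-defined list" and "the participants will be asked open questions at each session". Section 22 adds: "At each session the participants will answer questions of possible adverse events during and between the sessions". Between sessions, section 22 asks participants to phone the project physiotherapist about minor events and to seek care at once for serious ones.

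**Load.** The exercise descriptors in the appendix move seated heel-rise and elastic band from 15–20 RM to 15RM at week 6 or 7, and both exercises run to week 9.

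**The concern.** Active questioning follows the session calendar, and that calendar has two features that matter for counting minor events.

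First, arm B is seen more often than arm A in the early weeks. Section 12 makes the number of minor events an outcome, so part of any difference between arms in that count would reflect how often patients were asked.

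Second, the dated sessions stop before weeks 7–8, while the exercises continue. The monitoring board in section 21a grades all adverse events and can delay the intervention. A non-serious symptom that first comes up at the 9-week visit reaches the board when the exercise period is over and that option has little use.

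**Working it through.** The plan states no figure for contact frequency, so there is none to reproduce. The check is a calendar.

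**Convention.** Section 11a opens week 2 on day 7, so week k covers days 7(k−1) to 7k−1. Week 2 is days 7–13, week 3 is days 14–20, week 5 is days 28–34, week 6 is days 35–41, weeks 7–8 are days 42–55, and week 9 opens on day 56. The examination after 9 weeks is day 63.

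**Arm B.** The introduction falls on days 7–13 and the first booster one week later, on days 14–20. The second booster has two readings:
- Both intervals counted from the introduction: 7 + 21 = 28 to 13 + 21 = 34, which is week 5.
- Intervals in sequence (1 week, then 3 more): 7 + 28 = 35 to 13 + 28 = 41, which is week 6.

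Attending the standard week-6 booster would also put arm B's last session on days 35–41.

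**Arm A.** Day 14, then week 6 (days 35–41).

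Under every reading, no session falls on days 42–55 in either arm.

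**Gap after the last dated session**

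| Case | Last session | To day 63 | To day 56, if a week-9 group session counts |
|---|---|---|---|
| Arm B, last session in week 5 | days 28–34 | 63−34 = 29 to 63−28 = 35 | 56−34 = 22 to 56−28 = 28 |
| Arm B, last session in week 6 | days 35–41 | 63−41 = 22 to 63−35 = 28 | 56−41 = 15 to 56−35 = 21 |
| Arm A | days 35–41 | 22 to 28 | 15 to 21 |

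A symptom that starts in weeks 7–8 and is first asked about on day 63 is 63−55 = 8 to 63−42 = 21 days old.

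**Dated contacts before week 7**
- With the 2-week appointment counted in both arms, A has 2. B has 3 sessions + 1 = 4, or 5 with the standard week-6 booster. B has 3 if the first booster and the day-14 appointment are one visit and the week-6 booster is not attended. The difference is 3−2 = 1 to 5−2 = 3.
- With that appointment left out of both arms, A has 1 and B has 3, or 4 with the week-6 booster. The difference is 2 to 3.

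**Effect of a form on day 49.** For arm B with its last session in week 5, the intervals are 49−34 = 15 to 49−28 = 21 days, then 63−49 = 14, so the longest is 15–21. With the last session in week 6 (arm A, or arm B on that reading), they are 49−41 = 8 to 49−35 = 14 days, then 14, so the longest is 14.

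**The case against.** The strongest reply is that a missing date is not missing monitoring, and much of it stands.

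- Sections 13 and 18a promise close follow-up during the intervention, and the timeline draws complications as a continuous row. Section 18b keeps participants in usual outpatient follow-up. Those visit dates are not shown, so some may fall in weeks 7–8.
- Progression is gated on symptoms. The exercise schedule and the descriptors table allow a move to the next phase only without persistent pain or discomfort, and the schedule also requires that movements are not compensated. Section 11a holds exertion to 2–5 on the Borg scale.
- The load step is small: 15RM is the heavy end of the range already allowed. It can begin in week 6, when arm A has a booster and arm B may have one.
- The documents use the word session for follow-up visits too (section 18b; SAP section 5), and section 22 covers events between sessions. The 9-week visit can therefore ask about weeks 7–8. What is lost is timeliness and some recall, not the data.
- Extra contact is part of a supervised add-on. More questioning in arm B would tend to raise its count of minor events, so it would not hide harm there.

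A reader might infer that patients go unwatched while load rises, or that the trial is unsafe in those weeks. The documents do not support that, for the reasons above and because serious events have their own routes (sections 22 and 30). What survives is narrower: none of these routes puts the same question to both arms on the same date, and the early contact counts differ under every reading.

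**Conclusion.** The point holds as a modest gap in ascertainment. No exercise session is dated in weeks 7–8 in either arm. The gap to the 9-week examination is 22–35 days in arm B and 22–28 days in arm A. Arm B has 1–3 more dated contacts before week 7. The protocol's count of minor adverse events is therefore not like for like between arms, and non-serious symptoms in weeks 7–8 rest on a phone call, an undated clinic contact or recall.

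These figures assume the week numbering above, day 63 for the 9-week visit, and both readings of the booster timing. They measure spacing between contacts, not harm: the documents give no rate of minor events, so the number reported late or missed cannot be estimated.

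A reader might also take this as a threat to the main result. It is not. ATRS at 13 weeks does not depend on these questions, the SAP's adverse-event outcome (section 2.2, item 11) is limited to serious events, and SAP section 6.2 only describes secondary endpoints. The change is optional and worth making because it is cheap.

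**What to change.** - Send both arms one identical short REDCap form on the same day in weeks 7–8, for example day 49. It should hold section 11b's symptom questions and section 12's pre-defined adverse-event list.
- Add the same list to the existing 9-week REDCap link (section 9), worded to cover the whole exercise period since allocation. Count an event that appears on both forms once.
- Keep section 21a's rule that muscle soreness and mild pain are not adverse events, so that expected soreness in arm B does not inflate its count.
- Route positive answers to the project physiotherapist, then to the chief foot surgeon within section 30's times, and to the board for grading under section 21a.
- Report minor events by arm from these two common forms, and describe events elicited at sessions separately.

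The cost is protocol wording, one automated form per participant (82 in all) and one list on a link that already exists. No visit, assessor, exercise dose or clinical threshold changes. The downsides are slight participant burden, some follow-up calls and reliance on recall for the earlier weeks. The forms give both arms the same questions on the same dates, but they cannot undo the unequal questioning in weeks 2–6.
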